7.3 Height and Weight

Height or length (cm), and weight (kg) will be measured once and recorded on the eCRF.

7.4 Head Circumference

Head circumference (cm) will be measured and recorded on the eCRF.

7.5 Vital Signs

Vital signs (blood pressure, heart rate, respiratory rate, and temperature measurements) will be measured and recorded on the eCRF.

7.6 Electrocardiography

7.6.1 Electrocardiograms

An ECG will be performed. Each ECG will include an assessment of heart rate, sinus rhythm, atrial or ventricular hypertrophy, PR, QRS, QT, and QTc intervals. The ECGs will be conducted in accordance with the clinical site's standard practice(s), and will be read locally at the clinical site. Identification of any clinically significant findings and/or conduction abnormalities will be recorded on the eCRF.

7.7 Clinical Laboratory Tests

Blood, urine, and CSF samples will be collected as described below for clinical laboratory testing. Procedures for collection and handling of samples are included in the Laboratory Manual. The conduct of a clinical trial in an extremely rare disease such as MPS IIIA provides a unique opportunity to collect samples for potential biomarker research. In the context of this study, a biomarker is defined as a characteristic that is objectively measured and evaluated as an indicator of the MPS IIIA pathogenic process, or a pharmacologic response to experimental therapy with HGT-1410. In addition to exploration of potential biomarkers, as part of the assessment of the SOPH-A-PORT Mini S, it may be necessary to determine the levels of leachables from the device into the CSF and blood.

For patients who do not have the IDDD removed (partial or full device) at the end of the treatment period, clinical laboratory testing will only be performed when indicated for a device-related AE during the safety follow-up period.

Patients will be in a seated or supine position during blood collection. Clinical laboratory tests will include hematology, serum chemistry, and urinalysis.

Laboratory Parameters

Clinical laboratory tests will be performed at a central laboratory. Clinical laboratory tests will include the following:

7.7.1 Hematology

-
- | | |
|--|--|
| • Hematocrit (Hct) | • Mean corpuscular volume (MCV) |
| • Hemoglobin (Hgb) | • Platelet count |
| • Mean corpuscular hemoglobin (MCH) | • Red blood cell (RBC) count |
| • Mean corpuscular hemoglobin concentration (MCHC) | • White blood cell (WBC) count with differential |
-

7.7.2 Serum Chemistry

-
- | | |
|--|--|
| • Albumin (ALB) | • Glucose |
| • Alkaline phosphatase (ALK-P) | • Lactate dehydrogenase (LDH) |
| • Alanine aminotransferase (ALT; SGPT) | • Phosphorus |
| • Aspartate aminotransferase (AST; SGOT) | • Potassium (K) |
| • Blood urea nitrogen (BUN) | • Sodium (Na) |
| • Calcium (Ca) | • Total bilirubin |
| • Carbon dioxide (CO ₂) | • Direct bilirubin |
| • Chloride (Cl) | • Total cholesterol |
| • Creatinine | • Total protein |
| • Creatine kinase (CK) and subtypes | • Triglycerides |
| • Gamma-glutamyl transferase (GGT) | • Uric acid |
| • Globulin | • Human Chorionic Gonadotropin (βhCG) Pregnancy Test |
-

In addition a leukocyte pellet will be prepared, stored frozen, and will be used for additional disease-related laboratory studies, including possible assessment of cross-reactive immunologic material (CRIM).

7.7.3 Pregnancy Test

A pregnancy test will be performed on Day 1 of each dosing week. Pregnancy testing will be performed using either a serum or urine sample (at the discretion of the site), and only on females who have reached menarche. All pregnancy testing and the reporting of results will be performed locally by the clinical site staff. Study drug must not be administered in the event of a positive or inconclusive pregnancy result.

7.7.4 Serum Anti-rhHNS Antibody and Sample Storage

Blood samples will be collected and evaluated at Shire or Shire-designated laboratories for the determination of anti-rhHNS antibodies. Samples will be reserved in accordance with local regulations for potential future MPS IIIA research that may determine biomarkers of disease severity and progression.

Two blood samples will be collected from each patient at each designated time point. One sample will be collected in tubes intended for serum specimens, while the second sample will be collected in tubes intended for plasma specimens. Blood sample collection, processing, and shipping instructions will be provided in the Laboratory Manual.

7.7.5 Urinalysis

Patient catheterization may be required for obtaining urine samples (if deemed necessary by the investigator).

7.7.5.1 Standard Urinalysis

The following urinalysis parameters will be performed at a central laboratory: pH, macroscopic and microscopic evaluations.

7.7.5.2 Urine Glycosaminoglycans

A urine sample will be collected for the determination of GAG (including heparan sulfate and heparan sulfate derivatives) and the analysis will be performed at Shire, or Shire designated laboratories. A urine sample from each visit will be reserved for possible exploratory biomarker studies that may provide new indicators or markers of MPS IIIA disease severity or progression.

7.7.6 Cerebrospinal Fluid Assessments

Cerebrospinal fluid sample collection, processing, and shipping instructions will be provided in the Laboratory Manual. A CSF sample will be reserved for possible exploratory biomarker studies for MPS IIIA disease.

Each CSF sample collected will be assessed for appearance and will be analyzed using the assays listed in Sections 7.7.6.1, 7.7.6.2, and 7.7.6.4. In addition, as more is learned about Sanfilippo CNS pathology and etiology, future exploratory assays of CSF metabolites, protein or ribonucleic acid (RNA) may become used as they become available in the future.

7.7.6.1 Cerebrospinal Fluid Cell Counts

An aliquot of each CSF sample collected will be evaluated for CSF standard chemistries, glucose, protein, and cell counts. These assessments will be performed at the local laboratory.

7.7.6.2 Cerebrospinal Fluid Heparan Sulfate Levels and Heparan Sulfate Derivatives

An aliquot of each CSF sample collected will be quick frozen as per the Laboratory Manual for subsequent determination of CSF heparan sulfate and heparan sulfate derivatives at Shire designated laboratories.

7.7.6.3 Anti-rhHNS Antibodies

An aliquot of each CSF sample collected will be quick frozen as per the Laboratory Manual for subsequent determination of anti-rhHNS antibodies at Shire or Shire designated laboratories.

7.7.6.4 Cerebrospinal Fluid Biomarkers

An aliquot of each CSF sample collected will be quick frozen as per the Laboratory Manual for subsequent determination of MPS exploratory biomarkers at Shire or Shire-designated laboratories.

7.7.7 Sample Collection, Storage, and Shipping

Sample collection, processing, and shipping instructions will be provided in the Laboratory Manual to be provided by Shire.

CSF, urine, and serum samples may be reserved for potential, future, biomarker studies. Samples will be stored securely to ensure patient confidentiality.

7.8 Anesthesia

Administration of anesthesia/sedation will be given prior to obtaining CSF (when the use of the IDDD is precluded), prior to performing a MRI of the head, the ABR, the CSF opening pressure, and the partial revision or replacement of the IDDD (if applicable).

See [Appendix 1](#) for the Schedule of Events. When logistically feasible, the MRI, ABR, and surgical implantation of the IDDD may be performed together to reduce exposure to general anesthesia.

Note: The neurologic exam and the neurocognitive and developmental assessments must be performed prior to the administration of anesthesia.

7.9 Audiometry and Auditory Brainstem Response

[figure not shown]
The rare attenuated patients with MPS IIIA with high levels of cognitive functioning will have hearing tests via clinical audiometry measurement performed using age-appropriate testing methods based on the child's developmental age at the time of the testing. It is anticipated that most of the cognitively-impaired and/or behaviorally-deteriorated patients with Sanfilippo A will be unable to cooperate with a (conscious) hearing evaluation. In these instances, the investigator will utilize his best clinical judgment to estimate the extent of hearing loss (if any) during the physical examination. In this situation, a specific evaluation of hearing loss will occur during an examination of waveforms in the ABR (see below). If the patient has a history of multiple instances of otitis media or evidence of clinically-significant otitis media on physical examination, which the investigator believes causes significant conductive hearing loss and impairment of daily living, the investigator will discuss and offer the parent or legally authorized representative(s) placement of PE tubes as part of the scheduled anesthesia. A patient's PE tubes may be replaced if they fall out during the course of this study.

The ABR will be conducted under anesthesia. The ABR findings will be considered within normal limits if, after applying appropriate correction factors, the waveforms reveal normal morphology.

7.10 Magnetic Resonance Imaging of the Head

The regional brain volume will be assessed through a MRI, of the head. The patient will be under general anesthesia for this assessment. All MRIs will be centrally read by the University of Minnesota Medical Center. Refer to the Study Operations Manual for specific procedures and precautions.

7.11 Device Data

7.12 Surgical Re-implantation of the IDDD

If a patient's IDDD becomes nonfunctional or infected, it will be replaced or revised so that the patient can remain on study. After full approval of protocol Amendment 4, all IDDD replacements will be made with the SOPH-A-PORT IDDD. If the IDDD device is a PORT-A-CATH IDDD, it will be replaced by a SOPH-A PORT IDDD. Management details for the PORT-A-CATH IDDD or for the SOPH-A PORT IDDD are provided in the respective device's IFU. Procedures for implantation are detailed in the relevant device's Instructions for Use Manual and in the training materials provided by Shire. The patient will be under general anesthesia for this procedure. Standard hospital procedure for surgery will be followed and will include an X-ray to confirm that the device has been (1) surgically implanted correctly, and (2) positioned so that the intrathecal catheter tip is at the mid-thoracic level (a check list is provided in the IDDD Manual).

A post-operative check of the IDDD and incision will be performed on Day 4 following surgery. X-rays may be performed to check placement of the device, as needed, throughout the study (see Section 7.12.1 for limits on the number of x-rays and IDDD revisions and or replacement).

7.12.1 Restrictions on the Number of Revision and/or re-implantation of the IDDD

A non-functional IDDD can be replaced or revised twice in a 6-month period, including the time a patient was in study HGT-SAN-055. Similarly, 6 X-rays may be taken in a 6-month period (including the time in HGT-SAN-055).

7.13 Device Related Study Procedures

7.13.1 IDDD Implantation or Revision Procedures

The IDDD will be surgically implanted or revised at the clinical site. Procedures for implantation and revision are detailed in the device's IFU. Standard hospital procedures for surgery will be followed; the patient will be under general anesthesia for this procedure. It is planned that device explantation will occur at the main site unless urgent device removal is medically indicated requiring the procedure to be performed locally or patient travel to the main site is medically inadvisable.

An additional medical device, the catheter passer, is necessary for the implantation procedure, for patients receiving the SOPH-A-PORT Mini S. The catheter passer is a sterile, single use device that will be used in the subcutaneous placement of the catheter. The Phoenix Neuro Disposable Catheter Passer, manufactured by Sophysa is CE marked in the European Union (EU) and cleared under K853370 in the United States (US). Other catheter passers that are compatible with the SOPH-A-PORT Mini S may be used.

Details of the implantation/revision and malfunctions/failure for the SOPH-A-PORT will be documented on the patient's eCRF.

7.13.2 X-ray Verification of Intrathecal Drug Delivery Device Placement

A postoperative x-ray check of the IDDD will be performed following surgery to verify proper installation and confirmation of IDDD placement at the mid-thoracic level. The x-rays may be performed to check placement of the device, migration, or malfunction of the device as needed, throughout the treatment period or the safety follow-up period of the study. At a minimum, the date of the x-ray verifying correct IDDD placement will be documented on the patient's eCRF. If the device requires revision or replacement during the treatment period of the study, additional x-rays will be taken to document proper positioning of the device. If an IDDD malfunctions, an x-ray may be performed to assess the potential cause of malfunction. Fluoroscopy may be used during device implant or revision procedures.

7.13.3 CSF Sampling Procedure

Cerebrospinal fluid will be sampled via the device. If this is not possible, and if CSF sampling is necessary, either for adherence to the protocol, or to investigate clinical concerns, an LP may be performed to sample CSF, either with or without administration of drug afterwards.

7.13.4 Device Removal

If at the time of a scheduled dosing it is not possible to administer a full medication dosage as per the standard administration steps detailed in the device's IFU due to a device-related issue, the IDDD will be declared a device malfunction. If the device malfunction is irreversible and cannot be corrected without a device surgical intervention, the IDDD will be declared a device failure, starting from the date of the initial malfunction.

The IDDD will then be surgically removed or revised and a new device and/or device components will be re-implanted at the earliest possible opportunity, preferably at the same time.

Patients who have a PORT-A-CATH IDDD device failure will have this device replaced by a SOPH-A-PORT Mini S.

Details of the device removal will be recorded in the patient's eCRF. Refer to the relevant IFU for further details.

If the IT space is not accessible via the IDDD, study drug may be administered by LP up to 5 times.

Patients should have the IDDD removed when they discontinue from the treatment period of the study, unless the Investigator determines that it should not be removed based upon safety assessments. The device can remain in the patient (partial [catheter only] or full [port, catheter, and suture wings]) if the patient is doing clinically well and there are no further known risk factors such as infection (eg, meningitis). The device may be partially or fully removed as medically required and determined by the neurosurgeon at a future date.

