It is anticipated that the IDDD will be used to obtain CSF samples and to deliver administrations of HGT-1410. However, if a patient's IDDD appears nonfunctional or if its use is precluded on a scheduled day of dosing, site personnel will refer to the operations manual (for PORT-A-CATH) or the IDDD Manual (for SOPH-A-PORT), which describes the investigation and management of IDDD-related issues. This will include possible partial revision or complete replacement of the IDDD. As noted above, a maximum of 2 partial revisions and/or complete replacements can occur in any 6 month period. If revision or replacement of the IDDD cannot be scheduled in time to avoid a delay of the next scheduled dose of HGT-1410, or if the patient experiences more than 2 IDDD malfunctions in a 6 month period (including participation in study HGT-SAN-055), HGT-1410 will be administered via lumbar puncture (LP).

If there are medical contra-indications to the re-implantation of a new device, or if the patient so desires, repeat monthly lumbar punctures may be considered as an alternative way of delivering the study drug and obtaining CSF samples under limited circumstances. If no safety risks are identified by the investigator, up to 12 consecutive lumbar punctures may be performed across the studies HGT-SAN-055 and HGT-SAN-067. Once a patient has reached the maximum of 12 consecutive lumbar punctures, a new IDDD may be re-implanted for subsequent dosing, unless, in the opinion of the investigator and medical

monitor, assessment of risk/benefit favors continued dosing via lumbar puncture.

Continued treatment via lumbar puncture beyond the stipulated 12 consecutive monthly doses can be considered only in individual cases where this treatment is very well tolerated and the investigator has not identified any safety concerns associated with repeat lumbar puncture and repeat sedation/anesthesia.

During the treatment period, if there was no significant safety risk in the opinion of the investigator, a non-functional IDDD may have been left in situ for up to 3 months.

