If the patient is discontinued from the study, the IDDD should be removed and a modified end of study visit should be completed within 30 days after withdrawal. These visits may be combined into one visit, in which case follow-up via a phone call should be completed within 14 days after the device removal to collect safety information. If the investigator determines that the IDDD should not be removed from the patient based upon a safety assessment and the IDDD (full or partial) remains in the patient, then the patient will continue in the study under the safety follow-up period upon completion of their last treatment period visit.

It is anticipated that the IDDD will be used to obtain CSF samples and to administer HGT-1410. However, if a patient's PORT-A-CATH IDDD appears nonfunctional or if its use is precluded on a scheduled day of dosing, site personnel will refer to the PORT-A-CATH Instructions for Use (IFU), which describes the investigation and management of IDDD-related issues with this device. This will include possible partial revision or complete replacement of the PORT-A-CATH IDDD with a SOPH-A-PORT IDDD. For malfunctions involving the SOPH-A-PORT Mini S, site personnel will refer to the SOPH-A-PORT IFU. For either IDDD, a maximum of 2 partial revisions and/or complete replacements are permitted in any 6 month period (including participation in study HGT-SAN-055). If a revision or replacement of the IDDD cannot be scheduled in time to avoid a delay of the next scheduled dose of HGT-1410, or if the patient experiences more than 2 IDDD malfunctions in a 6 month period, HGT-1410 will be administered via lumbar puncture (LP). If implantation of a replacement IDDD is not possible, investigational drug may be administered by LP for a maximum of 12 successive monthly doses. At that point, a safety discussion needs to take place between the investigator and the sponsor to determine the risk/benefit of further dosing by LP.

If there is no significant safety risk in the opinion of the investigator, a non-functional IDDD may be left in situ for up to 3 months during the treatment period.

Patients who discontinue or are withdrawn before receiving 3 monthly IT injections will not have to undergo the EOS evaluations but will have their IDDD removed.

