6.3 Selection and Timing of Dose for Each Patient

Patients will check into the study center 1 day prior to IT HGT-1410 dosing for safety assessments, designated Day 1, on each HGT-1410 treatment week, and if no safety concerns exist, will receive IT administration of HGT-1410 on Day 2 (± 2 days). However, if feasible and there are no safety concerns in the opinion of the investigator, the Day 1 and Day 2 assessments and dosing may be combined and performed on Day 2; if this is done the results will be recorded as Day 2. Patients will remain in the study center for at least 4 hours following dosing with HGT-1410 and will be discharged from the unit when deemed clinically stable by the investigator.

The IT injections are to be administered every 28 days (± 7 days). If a patient's IDDD becomes nonfunctional, it may be revised (partial or complete) (a maximum of twice in a 6 month period) so that the patient can remain on study (see Section 7.12 for details).

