In the event of IDDD malfunction, CSF collection and study drug administration may be performed via LP (see Section 6.3.2). The investigation and management of a malfunctioning IDDD is detailed in the PORT-A-CATH or SOPH-A-PORT IFUs. Partial or complete replacement of the IDDD may be necessary (only permitted twice in a 6-month period, including the time a patient was in study HGT-SAN-055), and will require scheduling of the appropriate procedure. The definitive diagnosis of the cause of IDDD failure may not be possible until the time of exploratory surgery. Surgery will take place at the earliest convenience, so the patient may remain on, or as close as possible to their treatment schedule.

6.3.2 Administration of HGT-1410 via Lumbar Puncture Guidance Concerning Performance of Lumbar Puncture for Study Drug Administration and Cerebrospinal Fluid Sample Collection

It is intended that the IDDD will be used to deliver all IT injections of study drug and to obtain CSF samples. If the IDDD appears to be nonfunctional, or if its use is precluded on a scheduled day of dosing, site personnel will refer to the IDDD manual (s), which provides details on the investigation and management of any IDDD-related issues. This may include possible partial revision or complete replacement of the IDDD as indicated. If the nonfunctional IDDD is a PORT-A-CATH device, then it will be replaced by a SOPH-A-PORT Mini S device.

If there are medical contra-indication to the re-implantation of a new device, or if the patient so desires, repeat monthly lumbar punctures may be considered as an alternative way of delivering

the study drug and obtaining CSF samples under limited circumstances. If no safety risks are identified by the investigator, up to 12 consecutive lumbar punctures may be performed across studies HGT-SAN-055 and HGT-SAN-067. Once a patient has reached the maximum of 12 consecutive lumbar punctures, a new IDDD will be re-implanted for subsequent dosing, unless, in the opinion of the investigator and medical monitor, assessment of risk/benefit favors continued dosing via lumbar puncture.

Continued treatment via repeat lumbar puncture beyond the stipulated 12 consecutive monthly doses can be considered only in individual cases of patients where this treatment is very well tolerated and the investigator has not identified any safety concerns associated with repeat lumbar puncture and repeat sedation/anesthesia.

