7.15 Dispensing Study Drug

A visual examination of both the port and catheter track will be performed before each IT injection.

HGT-1410 will be administered IT by means of an IDDD (or via LP if necessary) to patients on Day 2 (± 2 days) of Week 1 of each treatment month.

The patient may be sedated for this procedure. HGT-1410 will be administered through an appropriately sized syringe (see the Pharmacy Manual). If the IT space is not accessible via the IDDD, HGT-1410 may be administered via LP. See Section 6.3.2 for details.

For the Soph-A-Port Mini S, a 22-gauge Huber non-coring needle is to be used for access to the implanted port; standard hypodermic needles would damage the septum and may cause leakage. If no needle-free connector is present, either a stopcock or the Huber needle infusion set's clamp is to be used to prevent CSF backflow and to mitigate the risk of air entering the system. It is possible to use other brands of Huber non-coring needles, provided that their specifications are identical to that of the Huber needle supplied by Sophysa in the SOPH-A-PORT Mini S (22G).

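### Section 7.13.4 allows dosing by lumbar puncture 5 times, while the Synopsis and Sections 4.1 and 6.3.2 allow 12 in a row, and the protocol states no scope that separates the two limits

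*Protocol*

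**What the plan says.** Four places in the current text (Amendment 8) put a number on dosing by lumbar puncture (LP).

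- **Section 7.13.4 (Device Removal)** defines device malfunction and failure and calls for removal or revision with re-implantation as early as possible. It then says: "If the IT space is not accessible via the IDDD, study drug may be administered by LP up to 5 times". It gives no counting rule, no next step after the fifth LP and no reference to another section.
- **Section 6.3.2** says "up to 12 consecutive lumbar punctures may be performed across studies HGT-SAN-055 and HGT-SAN-067". After 12, a new device *will* be re-implanted unless the investigator and medical monitor judge that risk and benefit favour staying on LP. It adds: "Continued treatment via repeat lumbar puncture beyond the stipulated 12 consecutive monthly doses can be considered only in individual cases", where LP is very well tolerated and raises no safety concern.
- **The Synopsis** has the same allowance, "up to 12 consecutive lumbar punctures may be performed across the studies HGT-SAN-055 and HGT-SAN-067", with the same exceptions but a softer default: "Once a patient has reached the maximum of 12 consecutive lumbar punctures, a new IDDD may be re-implanted for subsequent dosing".
- **Section 4.1** says "investigational drug may be administered by LP for a maximum of 12 successive monthly doses", after which investigator and sponsor discuss the risk and benefit of further LP dosing. It has no individual-cases wording and does not say whether doses in HGT-SAN-055 count.

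Two further places decide which rule a site will look up. Section 7.15 says: "If the IT space is not accessible via the IDDD, HGT-1410 may be administered via LP. See Section 6.3.2 for details". The last paragraph of Section 6.3.1 also refers drug administration after a device malfunction to Section 6.3.2.

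**The concern.** A site with a patient whose device no longer gives access finds 5 in the section on device failure and 12 in the section on LP dosing. Nothing in either says which prevails.

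Two things are at stake. The first is procedure burden in children. Section 7.8 provides anaesthesia or sedation before CSF is obtained when the device cannot be used. Section 7.22.1.4 says the device was chosen partly to avoid repeated anaesthesia for LP, and it lists serious risks for both LP and anaesthesia. The second is compliance. Section 11.9 requires every departure from the protocol to be documented as a deviation and grants no exemptions, so the status of a 6th to 12th LP dose has to be decidable from the text. At present it is not.

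**Working it through.** There is no sample size, power or error rate to reproduce. The check is a side-by-side reading plus simple arithmetic.

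**Step 1. The limits compared.**

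| Place | Limit | Counting | Trigger | Next step |
|---|---|---|---|---|
| 7.13.4 | 5 | not stated | intrathecal space not accessible through the device | none stated for LP dosing |
| 6.3.2 | 12 | consecutive, both studies | re-implantation contraindicated, or patient wish | device *will* be re-implanted unless risk/benefit favours LP |
| Synopsis | 12 | consecutive, both studies | as 6.3.2 | device *may* be re-implanted unless risk/benefit favours LP |
| 4.1 | 12 | successive monthly doses | replacement not possible | risk/benefit discussion |

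**Step 2. Do 5 and 12 govern separate situations?** The triggers differ in wording, but they overlap. A patient whose device gives no access and for whom re-implantation is contraindicated meets the trigger in 7.13.4 and the trigger in 6.3.2 together. Section 7.15 uses the trigger of 7.13.4 almost word for word and points to 6.3.2. Section 6.3.1 does the same for malfunction. A reader who follows either pointer finds 12 and never meets the 5.

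**Step 3. Size of the gap.** Inputs: 5 (7.13.4), 12 (6.3.2, Synopsis, 4.1) and a nominal interval of 28 days (6.3).

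- Procedures: 12 − 5 = 7.
- Time covered, counting each dose with the interval that follows it: 5 × 28 = 140 days and 12 × 28 = 336 days.
- Difference: 336 − 140 = 196 days. Counting from first to last dose gives the same difference: (11 × 28) − (4 × 28) = 308 − 112 = 196 days.
- Anaesthesia or sedation: up to 7 further episodes per patient, if each LP is done under it as Section 7.8 describes.

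**Step 4. Status of a given dose.** In one unbroken run, LP doses 1 to 5 are allowed everywhere. Doses 6 to 12 exceed 7.13.4 and are permitted under the Synopsis, 4.1 and 6.3.2 where their conditions are met.

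**The case against.** The strongest defence is that the two numbers serve different purposes. In 7.13.4 the sentence follows an instruction to re-implant as early as possible, so 5 could be a bridging limit. The 12 is tied to cases where re-implantation is contraindicated, unwanted or not possible. On this view the pointer from 7.15 settles little, because 6.3.2 opens with general guidance on a non-functional device and states the 12 only in a later, conditional paragraph.

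Part of this stands. The triggers are not identical, so the defect may be undefined scope rather than flat contradiction, and a repair could legitimately keep two limits. But the bridging reading is stated nowhere. Section 7.13.4 does not describe 5 as a bridge. Where the Synopsis and 4.1 do describe bridging (a replacement that cannot be scheduled before the next dose), they attach no number. The overlap in triggers also remains.

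Several stronger readings are tempting, and the documents do not support them:

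- **Total drug exposure.** A reader might infer that the lower limit means fewer doses. An LP dose is still a dose, no passage says dosing stops after the fifth, and 7.13.4 directs re-implantation.
- **A share of planned doses.** The 7 might be set against about 96 monthly doses. The protocol states no planned number of doses, and such a percentage would describe route of delivery, not lost treatment.
- **Device performance.** The summaries in Section 10.6.2.1 rest largely on first failure, first injection and failed injection attempts. It is not shown that 5 versus 12 LP doses after a failure would change them.
- **Three conflicting next steps.** The Synopsis, 4.1 and 6.3.2 all end in a risk/benefit judgement. Among them only the *may* versus *will* default differs.

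**Conclusion.** The point holds as a conflict, or at least an unresolved overlap, between current sections. One section gives 5 with no counting rule, three places give 12 in a row, and the protocol's own cross-references lead from the situation of the first to the rule of the others.

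The gap of 7 procedures rests on three assumptions: nominal 28-day dosing, a single unbroken run of LP doses, and the 5 being counted over that same run. If the 5 is cumulative over the study, the gap could be larger. The 12 is itself a conditional ceiling, since the Synopsis and 6.3.2 allow continuation in individual cases. The count of anaesthesia or sedation episodes is an upper figure, because Section 7.22.1.4 says only that patients may need anaesthesia before an LP.

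No statistical figure in the protocol changes. The weight of the point lies in invasive procedures in children and in whether a deviation can be identified.

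**What to change.** Reconcile Section 7.13.4 with the Synopsis and Sections 4.1 and 6.3.2 so that all four state:

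- one limit, or explicitly separate limits each with its own trigger;
- one counting rule: consecutive or cumulative, and whether LPs in HGT-SAN-055 count;
- one next step once the limit is reached, including whether a new device *may* or *will* be re-implanted.

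A cross-reference from 7.13.4 to 6.3.2 would stop the two drifting apart again. Which limit applies is a clinical decision for the sponsor and investigators, and this review does not propose one. The cost is amendment wording and a memo to sites. No new data and no change to the planned analyses are needed.
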